4.3 Protected populations

Prisoners

Due to the complexity of state and federal requirements governing the participation of prisoners in research, patients who are prisoners will not be considered for participation in this trial. In the unlikely event that a subject becomes a prisoner while participating in this trial, study procedures will stop and the subject will be returned to the clinical mode used prior to the intervention period or, if desired, an alternate mode requested by the clinical care team.

Pregnancy

Patients who are known to be pregnant will be excluded from participation.

5. Trial interventions

The intervention portion of this study is the randomized assignment (1:1) to receive quadratus lumborum block plus medical management or standard medical management alone. Randomization will be accomplished using an online service (www.randomizer.org) and prefilling sealed envelopes determining each subject's intervention group. Randomization will occur immediately prior to surgery. In all other aspects, the subject will receive the standard of anesthesia care appropriate for their surgery as determined by the primary anesthesia team caring for the subject. Preoperative medications will be left at the discretion of the in-room anesthesiologist for both pain and nausea regardless of the intervention.

5.1 Allocation to intervention

Randomization will be determined by opening a sequential, pre-sealed envelope with the group assignment designated within. Randomization will be accomplished using an online service (www.randomizer.org).

6. Subject recruitment and consent

6.1 Subject identification and Screening

When seeing patients for their preoperative consult, the surgical team will identify patients to be scheduled for laparoscopic ventral hernia repair. In addition, the operating room schedule will be reviewed to identify patients scheduled for laparoscopic ventral hernia repair. The medical records for those patients will be reviewed to identify patients that meet eligibility criteria. All protected health information used during the screening process of a potential subject will be the minimum necessary for the conduct of this study. Any PHI recorded for non-eligible patients, or patients that do not meet screening requirements will be destroyed immediately.

6.2 Recruitment and consent

For those patients meeting criteria, they will be approached by the anesthesiologist designated to care for them on the day of surgery. That anesthesiologist will then recruit the patient for the study in the pre-operative holding area. In order to ensure the candidate's privacy and confidentiality, the discussion will take place in pre-operative holding area with the cubicle's curtain and room door closed. In a tone of voice insufficient for others to overhear the conversation and in the presence of only those immediately accompanying the patient and those who are directly involved with the patient's care, the

candidate's eligibility will again be verified against the study enrollment criteria. For candidates with confirmed study enrollment eligibility, the study purpose, procedures, risks, benefits, and alternatives will then be discussed by a study staff member. The written information about the study provided to the candidate at the time of their check-in will be reviewed and they will be instructed to take up to 90 minutes to consider participation. A study member will conduct the informed consent discussion and obtain informed consent and a study physician will be available at all times for any consent-related questions. Any questions that the candidate may have will be answered. Undue coercion will be prevented by stressing that the potential subject does not have to agree to participation and that the future care of the potential subject will not change regardless of the decision about participation. If the candidate has no further questions and would like to participate, they will be asked to sign the written informed consent document.

7. Activities and measurements

Prior to the procedure:

The subject will be met in the preoperative area by a staff anesthesiologist, who interviews and examines the subject. A full explanation of general anesthesia and quadratus lumborum block, including risks, benefits, and alternatives, will be given and informed consent for anesthetic services obtained.

Subjects will be asked to rate their pain at rest using a Numerical Rating Scale (NRS) (0-10) where 0 represents no pain and 10 represents the worst pain imaginable.

Study Randomization:

After completion of pre-operative check in and consent is obtained by the staff anesthesiologist, the subject will be randomized to receive or not receive QLB. Randomization will be determined by opening a sequential, pre-sealed envelope with the group assignment designated within. If assigned to the intervention arm, they will then be prepped for QLB.

Quadratus Lumborum Block Procedure:

The block will be performed in the preoperative holding room as is standard practice at UW Health at the American Center. An intravenous catheter will be placed, and the subject will be pre-medicated with midazolam and/or fentanyl as needed at the discretion of the staff anesthesiologist.

Quadratus lumborum blockade will be performed after positioning the patient in the lateral decubitus position with the assistance of ultrasound guidance in the mid-abdomen posterior to the mid-axillary line. A Stimuplex needle (B. Braun Medical Inc., Melsungen, Germany) will be inserted in-plane to the ultrasound probe until the tip of the needle is appropriately positioned. Thirty milliliters of 0.25% bupivacaine will be injected under ultrasound guidance after negative aspiration. The procedure will then be repeated on the opposite side, maintaining sterility and, again, injecting 30 mL of 0.25% bupivacaine. The Bupivacaine mixture will be mixed with 2.5mcg epinephrine/ml of solution as an intravascular marker which is standard in most peripheral nerve blocks. In a situation where a patient is less than 60kg, a weight-based adjustment will be made to adjust dosing to the clinically accepted standard of 0.25mg/kg of bupivacaine. In the rare event that sonographic views are unobtainable, the patient will be excluded from the study. This outcome is unlikely to be clinically significant as qualification for laparoscopic ventral hernia repair has its own cutoff for body mass index and blocks are very rarely abandoned. However, for patient safety, we reserve the right to abandon a block.

During the Surgical Procedure:

In the operating room and in the procedural suite, monitors will be applied to the subject per established American Society of Anesthesiology (ASA) guidelines. At a minimum, these include non-invasive monitoring of blood pressure by automated cuff, oxygen saturation via pulse oximetry, heart rate and rhythm by 5-lead continuous electrocardiographic (ECG) tracing, core body temperature and expired carbon dioxide concentration. Additional monitoring may be applied on a case-by-case basis as deemed appropriate by the attending anesthesiologist. General anesthesia will be induced and endotracheal intubation will be performed by the in-room anesthesia team. Anesthetic care, including analgesics and antiemetics, will be administered per their discretion and extracted from the medical record.

Post-Procedure:

The patient will be visited in the PACU to assess pain satisfaction with perioperative care. Additionally, the following standard of care assessments will be completed: pain, opioid consumption, nausea, duration of PACU stay, and location of most severe pain. This information will be ascertained by questioning the patient and reviewing the subject's medical record.

For patients that underwent QLB, numbness to ice will be assessed. For this assessment, a plastic glove filled with ice water will be used to systematically assess for numbness too cold in the thoracic and lumbar dermatomes.

Postoperative analgesia will generally consist of scheduled acetaminophen, scheduled ibuprofen, oxycodone or hydrocodone PRN or any combination of these. Therapy may be altered for patients with history of drug intolerances or allergies or any other contraindication to a specific therapeutic agent. Analgesic therapy represents standard of care and is not altered by study involvement.

24 hours, 48 hours, and 7 days post-operative follow-up:

The patient will be contacted via phone at 24 hours, 48 hours, and 7 days to assess satisfaction with regional anesthesia, pain at rest, pain with activity, opioid consumption, nausea, pain disturbing sleep, and location of most severe pain. Duration of hospitalization will be obtained from review of medical record. Subjects with new or persistent complaints at 7 days post-surgery that could be related to the study procedures will be offered continued follow-up by telephone. Follow-up procedures would depend greatly on the clinical presentation but could include imaging, specialist consultation or surgical intervention. Subjects without complaints will be given appropriate information for contacting the research team if such complaints arise.

Concomitant Medications:

Analgesic and anti-emetic requirements for block placement, intraoperatively, and in PACU will be extracted from the patient's electronic medical record.

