10.1 Adverse event definitions	15
10.2 Severity assessment	16
10.3 Causality assessment	16
10.4 Procedures for recording and reporting adverse events	16
10.5 Other reportable events	16
11. Trial safety monitoring	17
11.1 Data Safety Monitoring Committee	17
12. Administrative requirements	18
12.1 Good clinical practice	18
12.2 Data quality assurance	18
12.3 Study monitoring	18
12.4 Ethical consideration	18
12.5 Patient confidentiality	18
12.6 Investigator compliance	18
12.7 Subject cost and payment	19
13. Funding sources	19
14. Publication Policy	19
References	20

Schedule of activities

	Screening/ Recruit/ Procedure Visit 1	PACU Visit 2	24 hours Post-op Visit 3	48 hours Post-op Visit 4 (Inpatient/ Phone)	7 days Post-op Visit 5 (Phone)
Window	Morning of Surgery	Following surgical procedure	24 hours post-op +/- 6 hours	48 hours post-op +/- 6 hours	7 days post-op +/- 6 hours
Screening and Eligibility	X				
Informed Consent	X				
Demographics	X				
Medical History	SOC				
Randomization	X				
Quadratus Lumborum Block	X				
Standard Medical Management	SOC				
Numbness Testing ¹		X			
Pain Questionnaire ²		X	X	X	X
Concomitant Medications ³	SOC	X	X	X	X
Adverse Events	SOC	SOC	X	X	X

¹Temperature sensation will be examined using a cold sensory technique

² Pain at rest, pain with activity, opioid consumption, nausea, location of most severe pain and satisfaction with regional anesthesia technique will be assessed

³Medications that are taken at home regularly and prior to arrival on the day of surgery, surgery premedication, and all medications for nausea and pain will be recorded.

List of abbreviations and definitions

AE	Adverse event
DSMC	Data Safety Monitoring Committee
PACU	Post-Anesthesia Care Unit
POD	Post-Operative Day
QLB	Quadratus Lumborum Block
SAE	Serious Adverse Event

1. Introduction

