1.2 Rationale and hypothesis

Thousands of patients undergo ventral hernia surgery each year. Quadratus lumborum blocks are a relatively new approach for providing analgesia to the abdominal wall. The effectiveness of quadratus lumborum blocks in reducing pain, opioid consumption, and time to discharge has not been evaluated for this surgery. We propose a prospective, single-center, randomized trial to evaluate the impact of quadratus lumborum block on patient recovery profile when performed for laparoscopic ventral hernia repair compared to a standard medical management. Standard medical management typically includes perioperative multimodal analgesia utilizing acetaminophen, opioids, non-steroidal anti-inflammatory drugs, and dexamethasone. Peripheral nerve blocks, as are offered in our study, are typically offered to patients but are not routinely performed secondary to time constraints in the operating room and surgeon or patient preference. The primary outcome of the study is pain at rest on POD1. Secondary outcomes will include pain at rest on POD 0, 2 and 7, pain with activity on POD 0, 1, 2 and 7; opioid consumption on POD 0, 1, 2 and 7; nausea in PACU; time to hospital discharge and patient satisfaction.

2. Objectives

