2.2 Secondary outcomes and endpoints

The secondary outcomes of this study are to compare the following perioperative variables:

Preoperative Variables:

- Baseline pain

Intraoperative Variables:

- Opioid consumption
- Additional analgesics
- Anti-emetic administration

PACU Variables:

- Pain at rest
- Pain with activity
- Nausea
- Numbness distribution
- Opioid consumption
- Time in PACU (duration)
- Time to discharge home (duration)
- Location of most severe pain

POD 1, 2, and 7 Variables:

- Pain at rest

- Pain with activity
- Opioid consumption in morphine equivalents
- Nausea necessitating treatment
- Location of most severe pain
- Satisfaction with perioperative care

3. Study design

This study is a prospective, single-center, randomized trial in which 48 subjects will be enrolled at the University of Wisconsin Hospitals and Clinics (UWHC). The details of the power analysis can be found below. These subjects must meet study eligibility criteria and be scheduled to undergo an elective laparoscopic ventral hernia repair. These subjects must also agree to undergo quadratus lumborum block for postoperative analgesia. Patients will be randomized to receive QLB in addition to medical management or medical management alone. Recovery characteristics, including pain scores, nausea, opioid consumption, duration of time in PACU and to discharge, will be evaluated.

4. Study population

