7.2 Subject withdrawals

At any point prior to or during the intervention period, the subject's clinical care team or a study physician may decide the subject should be withdrawn from the study. Additionally, a subject may at any point elect to withdraw themselves from the study. If a subject is withdrawn from the study for any reason the subject will then be followed according to standard of care follow-up.

Study intervention will immediately stop and subject's clinical care team and a study physician will be immediately notified if the subject suffers a severe adverse perioperative outcome.

In the event the study method is terminated, the reason for termination will be documented on a case report form.

8. Data analysis and statistical considerations

All data will be summarized using standard descriptive statistics, including mean, standard deviation, minimum, maximum, median, inter-quartile range, and confidence intervals, as appropriate. The data will be presented graphically (where possible) using scatter plots, profile plots, or histograms. Data analyses will be performed on an intent-to-treat basis based upon assignment to a treatment arm using SAS (SAS Institute Inc., Cary, NC; version 8.2 or greater) or other statistical software. The primary analysis will consist of comparing the two groups for superiority. For all tests, statistical significance will be defined as a p-value less than 0.05. Repeated measures ANOVA will be used to analyze comparisons made across multiple time points. Patients with missing longitudinal data will be handled by either using data imputation methods to replace the missing data or via alternative analyses tolerant of missing data values. Holm-Bonferroni correction will be used to control familywise error rates for comparisons across multiple time points.

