8.1 Sample size determination

The primary outcome for this study will compare resting NRS pain scores on POD1 between the QLB and medical management groups. A previous study of laparoscopic ventral hernia surgery reported an average POD1 pain score of 4.5 +/- 2.2 NRS (Fields et al, 2015). This average pain score is in keeping with our experience with patients after having laparoscopic ventral hernia surgery at UW-Madison. We feel that a reduction in pain of 2 NRS on POD1 would be meaningful for patients and their physician teams. Therefore, we will power this study to an effect size of 2 NRS. We will accept a type 1 error rate of 0.05 and 80% power. Using these metrics, the study will require a sample size of 21 patients in each group to

detect a statistical difference. To account for patients dropping out or not completing the study, we will enroll 24 patients in each group for a total of 48 patients.

9. Risks and benefits of trial participation

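### Pain with activity is compared at four postoperative times without a preoperative activity score, and the schedule omits the baseline pain score that Sections 2.2 and 7 call for (minor)

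*Combined protocol and SAP*

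**What the plan says.** Section 1.2 lists among the secondary outcomes "pain with activity on POD 0, 1, 2 and 7". Section 2.2 repeats pain with activity for the PACU and for POD 1, 2 and 7.

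Only one preoperative score is described, in Section 7 under *Prior to the procedure*: "Subjects will be asked to rate their pain at rest using a Numerical Rating Scale (NRS) (0-10". It stands ahead of the randomization step. Section 2.2 has a preoperative variable, "Baseline pain", and does not say whether this is rest, activity or both.

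In the schedule of activities, the row "Pain Questionnaire ²" is marked at PACU, 24 hours, 48 hours and 7 days. Its Visit 1 cell is empty, and no other row names baseline pain. Footnote 2 gives the content of that questionnaire: "Pain at rest, pain with activity, opioid consumption, nausea, location of most severe pain and satisfaction with regional anesthesia technique will be assessed".

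Section 8 describes the analysis in two sentences that matter here: "The primary analysis will consist of comparing the two groups for superiority" and "Repeated measures ANOVA will be used to analyze comparisons made across multiple time points". Neither names a baseline covariate, and nor does the rest of the section. Section 8.1 fixes the primary endpoint as resting pain: "The primary outcome for this study will compare resting NRS pain scores on POD1 between the QLB and medical management groups".

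**The concern.** There are two separate gaps.

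The first is in measurement. Patients differ in how much a hernia hurts on movement before it is repaired, and part of that difference may carry through to activity pain afterwards. With 21 to 24 patients per arm, a preoperative activity score would let the analysis remove some of this variation and would show whether the arms were alike at the start. No such score is described.

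The second is a disagreement within the protocol. Sections 2.2 and 7 expect a baseline pain score, but the schedule has no place for one. If the case report form or the visit checklist is built from the schedule, the resting score could be missed too, and that is the matching baseline for the primary endpoint.

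Both gaps have to be closed before enrolment. Consent, envelope, block and surgery follow one another on the same morning, and a preoperative score not taken then cannot be recovered by analysis.

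**Working it through.** **Which score is taken when**

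| Source | Before surgery | PACU / POD 0 | POD 1, 2, 7 |
|---|---|---|---|
| Section 2.2 | baseline pain, type not stated | rest and activity | rest and activity |
| Section 7 | rest only | pain, type not stated | rest and activity |
| Schedule and footnote 2 | no entry | rest and activity | rest and activity |

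The three sources do not agree on the preoperative column, and none of them expressly calls for an activity score there.

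**The plan's own sample size**

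Inputs from Section 8.1: difference 2 NRS, SD 2.2, type 1 error 0.05 (taken as two-sided), power 80%. A two-sample t-test (noncentral t) gives n = 20.002, rounded up to 21 per group, which matches the plan. Power at 21 is 82.0%. The 24 enrolled per group correspond to a loss of 1 - 21/24 = 12.5%. This calculation concerns resting pain on POD 1 without baseline adjustment, so the missing activity score does not affect it.

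**What adjustment could gain for activity pain**

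The documents give neither an SD for activity pain nor a baseline-outcome correlation r. I borrow SD = 2.2 from POD 1 pain and assume r between 0.3 and 0.5.

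- Unadjusted: SE = 2.2 × √(2/21) = 0.679. The 95% half-width is t(40) × 0.679 = 2.021 × 0.679 = 1.37.
- Adjusted: SE = 0.679 × √(1 - r²), with 39 degrees of freedom.
  - r = 0.3: SE = 0.648, half-width 2.023 × 0.648 = 1.31.
  - r = 0.5: SE = 0.588, half-width 2.023 × 0.588 = 1.19.

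The reduction is 1.37 - 1.31 = 0.06 to 1.37 - 1.19 = 0.18 points. For a 2-point difference at a single time, power goes from 82.0% to 85.4% (r = 0.3) or 91.3% (r = 0.5). The formula leaves out the small extra variance from whatever baseline imbalance occurs, so it slightly flatters the gain.

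**Gain over the resting score**

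The comparison above is with no adjustment at all. If the resting score is collected and used, the relevant gain is the difference between the two adjusted half-widths. Within the assumed range it is largest when the resting score has r = 0.3 and the activity score r = 0.5: 1.31 - 1.19 = 0.12 points. It is zero if both correlate equally with the outcome.

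**Chance imbalance**

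With 21 per arm, the 95% range for a baseline difference between arms is ±1.96 × √(2/21) = ±0.60 SD. How often the gap reaches 1 NRS point depends on the SD of preoperative activity pain, which is unknown:

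| Assumed SD | SE = SD × √(2/21) | Probability of a gap of 1 point or more |
|---|---|---|
| 2.2 | 0.679 | 14% |
| 1.5 | 0.463 | 3% |
| 1.0 | 0.309 | 0.1% |

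If the SDs before and after surgery are equal, a 1-point gap moves the outcome difference by r × 1 = 0.3 to 0.5 points.

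**The case against.** A reader might infer that activity pain can never be adjusted for pain present before surgery. The documents do not support that. Section 7 takes a resting NRS ahead of randomization, and a covariate need not be the same measure as the outcome. The resting score would capture part of the variation, and the baseline item in Section 2.2 is worded openly enough to leave room for an activity score.

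A reader might also infer that the activity-pain comparisons are biased. They are not: allocation is randomized 1:1, and chance imbalance is already reflected in the standard error and the type 1 error of an unadjusted comparison.

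It can further be said that the schedule gap is editorial. The questionnaire in footnote 2 contains follow-up items such as satisfaction with the block, so an empty Visit 1 cell for that instrument is reasonable. Section 7 asks for the resting score in plain terms, and this is a single-center trial whose staff must know the protocol. That is fair, and it would be speculation to say that the resting score will be missed. The schedule still has no row in which the score appears.

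Finally, no planned analysis uses a baseline score, so adding the item changes nothing unless Section 8 changes too. That is correct, and the fix therefore includes Section 8.

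What stands is narrower: the closest baseline for four planned comparisons is not collected, and the protocol disagrees with itself about whether any baseline pain score is taken at Visit 1.

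**Conclusion.** The point holds as a minor one. The four activity-pain comparisons cannot be adjusted for the patient's own preoperative activity pain, and the resting score replaces it only in part. The schedule must be reconciled with Sections 2.2 and 7.

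The loss is precision and a descriptive check on balance. Under the assumptions above, it amounts to 0.06 to 0.18 points of CI half-width compared with no adjustment, and to at most 0.12 points compared with adjusting for the resting score. The plan regards 2 points as meaningful. These figures rest on a borrowed SD and assumed correlations; they are illustrations and do not predict this trial's results. The primary endpoint has a matching resting baseline in Section 7, and the sample size is unaffected.

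**What to change.** 1. Section 7: at Visit 1, before the envelope is opened and before any premedication, record NRS pain at rest and NRS pain with activity.
2. Schedule of activities: add a row, *Baseline pain (rest and activity NRS)*, marked at Visit 1. A separate row avoids applying the follow-up items of the questionnaire before surgery.
3. Section 2.2: define the preoperative pain variable as these two scores.
4. Section 8: pre-specify the matching baseline score as covariate, that is, the activity baseline for the activity-pain comparisons and the resting baseline for the resting-pain comparisons.

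The cost is one further 0-10 question in an interview that already takes place, a schedule entry, and one degree of freedom in each model. No change in sample size is needed.

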9.2 Mitigation of potential risks

Regarding QLB: The risks of QLB will be minimized by carefully controlling the dose of bupivacaine and performing the block under ultrasound guidance allowing visualization of local anesthetic spread and avoiding intravascular injection. These procedures are performed under the supervision of an anesthesiologist that has subspecialized in regional anesthesia. The standard of care includes sterilizing the field of the block, using sterile equipment including gloves and needles to minimize the risk of infection. Ultrasound guidance allows us to identify all important adjacent structures during the procedure to avoid injury to adjacent tissue and blood vessels. In general, complications from peripheral nerve blockade such as the QL block are very rare.

Regarding Pain: The risk of inadequate analgesia will be minimized by the availability of supplemental oral and intravenous analgesics.

Confidentiality will be protected to the extent possible, by coding subject data and storing electronic data on a password-protected anesthesiology department network computer and hard copy data (source documents, signed consent forms, CRFs) in a locked study office.

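### The bupivacaine rule for patients under 60 kg (0.25 mg/kg) does not meet the fixed bilateral dose, which is 2.5 mg/kg at 60 kg, so the written dose drops tenfold at the threshold

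*Combined protocol and SAP*

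**What the plan says.** The block procedure in Section 7 (Activities and measurements, Quadratus Lumborum Block Procedure) sets a fixed dose for the first side: "Thirty milliliters of 0.25% bupivacaine will be injected under ultrasound guidance after negative aspiration". The second side is treated the same way, "maintaining sterility and, again, injecting 30 mL of 0.25% bupivacaine".

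The paragraph then makes an exception for light patients. It opens with "In a situation where a patient is less than 60kg" and continues "a weight-based adjustment will be made to adjust dosing to the clinically accepted standard of 0.25mg/kg of bupivacaine". It does not say whether the mg/kg figure is the total for both sides or the dose for each side.

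Section 9.2 names dose as a safeguard: "The risks of QLB will be minimized by carefully controlling the dose of bupivacaine". No other section states a mg/kg figure or a maximum dose. Sections 4.1 and 4.2 set no lower weight limit, so patients under 60 kg are eligible.

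**The concern.** A weight adjustment that takes over from a fixed dose at a threshold should give about the same dose at that threshold. Here the fixed dose and the adjusted dose appear to differ by an order of magnitude at 60 kg.

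Two things are at stake.

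- **Dose control.** The lightest patients are those the exception is written for, and for them the written figure cannot serve as the safeguard that Section 9.2 describes. The anesthesiologist must either follow it and give a very small block, or set it aside and choose a dose for which the protocol states no ceiling. Setting it aside would also depart from the approved protocol in the sense of Section 10.5.
- **Consistency of the treatment.** Section 8 analyses patients by assigned arm. Under the written rule, block-arm patients just below and just above 60 kg would receive materially different treatments and be counted together.

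**Working it through.** **Inputs, all from Section 7:** 30 mL per side, two sides, 0.25% bupivacaine, threshold 60 kg, adjusted dose 0.25 mg/kg. A 0.25% solution contains 2.5 mg/mL.

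**Fixed dose**

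- Per side: 30 mL × 2.5 mg/mL = 75 mg.
- Total: 2 × 75 mg = 150 mg.
- Per kg: 150/60 = 2.5 mg/kg at 60 kg; 150/80 = 1.875 mg/kg at 80 kg; 150/100 = 1.5 mg/kg at 100 kg.

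The protocol describes 0.25 mg/kg as an accepted standard, yet its own fixed dose is 10 times that figure at 60 kg (2.5/0.25) and 6 times at 100 kg (1.5/0.25).

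**Adjusted dose, read as the total for both sides**

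| Weight | Total dose (0.25 mg/kg) | Volume per side at 0.25% | 150 mg ÷ adjusted dose |
|---|---|---|---|
| 59.9 kg | 14.975 mg | 3.0 mL | 10.0 |
| 59 kg | 14.75 mg | 2.95 mL | 10.2 |
| 50 kg | 12.5 mg | 2.5 mL | 12.0 |

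**Other readings, at the threshold**

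- 0.25 mg/kg per side: 2 × 0.25 × 60 = 30 mg in total, and 150/30 = 5. The gap is fivefold.
- 0.25 mL/kg per side, as if the unit were wrong: 2 × 0.25 × 60 × 2.5 = 75 mg in total, and 150/75 = 2. The gap is twofold.

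None of the three readings meets the fixed dose at 60 kg.

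**What would meet it**

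A total of 2.5 mg/kg gives 2.5 × 60 = 150 mg, exactly the fixed dose. Below the threshold it gives 147.5 mg at 59 kg (29.5 mL per side) and 125 mg at 50 kg (25 mL per side), with no step. This points to a misplaced decimal. The inference uses only the protocol's own numbers, not an outside dosing standard.

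**Possible effect on the primary comparison**

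Section 8.1 plans for a difference of 2 NRS with SD 2.2, two groups, alpha 0.05 and 80% power, and reports that "the study will require a sample size of 21 patients in each group". A two-sided t-test with those inputs gives n = 20.0016, rounded up to 21 per group, so that figure reproduces and does not depend on the dosing rule.

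As an illustration, assume that k of n block-arm patients are under-dosed and lose the whole benefit, with the SD unchanged. The mean difference becomes 2 × (1 − k/n).

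| k | Power, 24 per arm | Power, 21 per arm |
|---|---|---|
| 0 | 0.87 | 0.82 |
| 1 | 0.84 | 0.78 |
| 2 | 0.81 | 0.74 |
| 3 | 0.77 | 0.69 |

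The documents do not give k, so this is a range and not a forecast.

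**The case against.** The strongest defence accepts the arithmetic and disputes the consequence.

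- **The two rules never apply to the same patient.** The fixed dose is the general rule and the mg/kg rule replaces it below 60 kg. That is true, so what is shown is a step at the threshold and not two instructions for one patient. But the sentence presents itself as an adjustment of the regimen, and the protocol gives no reason why a patient 0.1 kg lighter should receive a tenth of the drug.
- **It is probably a decimal slip that an expert would catch.** Section 9.2 places the block under an anesthesiologist subspecialized in regional anesthesia, who would probably query 3 mL per side against 30 mL. This lowers the chance of literal compliance. It does not correct the text or tell that anesthesiologist which dose to give.
- **The literal error is an under-dose.** The direct result would be an inadequate block, not excess exposure, and Section 9.2 provides supplemental oral and intravenous analgesics. This stands, and it limits the harm that can be claimed from following the text.
- **Few patients may be affected.** The number is unknown, cannot exceed the 24 in the block arm, and could be zero. One or two such patients would weaken the comparison modestly, toward no difference, and would not invalidate it. This also stands.

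These points limit the consequence. None of them makes the printed dose right.

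**Conclusion.** The concern holds and the text must be corrected. As written, the dose goes from 150 mg (2.5 mg/kg) at 60 kg to 14.975 mg (0.25 mg/kg) at 59.9 kg. The step is tenfold if the mg/kg figure is a total, which is the natural reading of the sentence, and fivefold if it is per side. The result rests only on the figures in Section 7 and the conversion 0.25% = 2.5 mg/mL.

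The case for correction is that the protocol misstates the dose of its only study intervention, a dose that Section 9.2 relies on as a risk control, and that nothing elsewhere supplies the right figure. It does not depend on demonstrated harm or bias. The number of patients under 60 kg is not known, and the sample size calculation is unaffected.

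**What to change.** The sponsor should reconcile the block paragraph in Section 7 so that the fixed volume and concentration, the 60 kg threshold and the mg/kg figure give the same dose at the threshold. The text should state whether the mg/kg figure is the total for both sides or per side; without that, even a corrected number could be applied at doses that differ twofold.

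The protocol's own numbers point to 2.5 mg/kg in total, but the clinical figure is for the sponsor to confirm and is not prescribed here.

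If enrolment is open, the corrected text should reach the block team before any further patient under 60 kg is treated. If such patients have already been treated, the dose each one received should be established from the medical record.

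The cost is a one-sentence amendment with the written IRB approval that Section 12.6 requires. Sample size and analysis do not change.
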